2.2 Secondary Objectives & Endpoints

2.2.1 To evaluate the safety and tolerability of nivolumab and veliparib in patients with advanced refractory solid cancers and lymphoma with and without mutations in selected DNA repair genes.

The endpoint will be the number, frequency, and severity of adverse events (as defined by the NCI CTCAE v4.03).

2.2.2 To evaluate the efficacy of treatment with nivolumab and veliparib in this population by objective response rate (ORR, defined as partial response (PR) + complete response (CR)), clinical benefit rate (CBR, defined as stable disease (SD) for ≥ 12 weeks, PR, + CR), and Progression Free Survival (PFS, defined as the time from treatment initiation to documented disease progression) using RECIST criteria v1.1 or Lugano criteria.

For the preliminary efficacy analysis, ORR will be done at the first imaging (8 weeks). Preliminary efficacy will be evaluated by RECISTv 1.1. As exploratory analysis, irRECIST will be used to obtain preliminary efficacy as well. All ORR will use the first imaging time point whether RECIST or irRECIST.

2.2.3 To evaluate efficacy of treatment with nivolumab and veliparib in this population by ORR, CBR, and immune-related PFS (irPFS) using irRECIST criteria.

2.2.4 To evaluate Overall Survival (OS) in this population at 3 years from the start of treatment. OS is defined as the time from treatment initiation until death due to any cause.

2.2.5 To evaluate the proportion of patients alive and progression free at 24 weeks in this population.

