6.1.7 Response criteria

- **Complete Response (CR)** - Disappearance of all target lesions. Any pathological lymph nodes (whether target or non-target) must have reduction in short axis to < 10 mm.
- **Partial Response (PR)** - At least a 30% decrease in the sum of the diameters of target lesions, taking as reference the baseline sum diameters.
- **Objective Response Rate** – the sum of complete responses and partial responses
- **Progressive Disease (PD)** - At least a 20% increase in the sum of diameters of target lesions, taking as reference the smallest sum on study (this includes the baseline sum if that is the smallest on study). In addition to the relative increase of 20%, the sum must also demonstrate an absolute increase of at least 5 mm. (Note: the appearance of one or more new lesions is also considered progression.)
- **Stable Disease (SD)** - Neither sufficient shrinkage to qualify for PR nor sufficient increase to qualify for PD, taking as reference the smallest sum of diameters while on study.

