10.0 STATISTICAL CONSIDERATIONS

10.1 Study Design/Study Endpoints

This will be a phase I/IB study of nivolumab and veliparib in patients with advanced solid tumors and lymphoma harboring mutations in selected DNA repair genes.

The **primary endpoint** is to evaluate the toxicities and tolerability of nivolumab and veliparib and to identify the maximum tolerated dose for combination treatment.

Secondary endpoints include ORR according to irRECIST, PFS at 24 weeks, time until death or disease progression, and to identify additional predictive biomarkers and resistance mechanisms to treatment using additional genetic and immunology-based assessment platforms. For the preliminary efficacy analysis, ORR will be computed at the first imaging (8 weeks). Preliminary efficacy will be evaluated by RECISTv 1.1. As exploratory analysis, irRECIST will be used to obtain preliminary efficacy as well. All ORR will use the first imaging time point whether RECIST or irRECIST.

Exploratory endpoints include biomarkers predictive of response include assessment of tissue-based immunohistochemical expression of PD-L1; TILs; peripheral T cell subpopulations; changes in tissue and peripheral T cell receptor sequencing, HLA genotype, and immune-related candidate gene signatures at baseline.

Pharmacodynamic biomarker assessment will include changes in tissue based immunohistochemical expression of PD-L1; TILs; peripheral T cell subpopulations, and T cell receptor genotype at baseline and after two months of treatment with veliparib and nivolumab.

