10.3 Data Analyses Plans

The primary analysis will be on the intent-to-treat (ITT) population, including all evaluable patients. Clinical benefit rate will be defined as stable disease (for ≥ 12 weeks), complete or partial response by both the Response Evaluation Criteria in Solid Tumors (RECIST) and irRECIST or Lugano Criteria 2014. Maximum response prior to disease progression will be used. The overall response rate will be estimated by the proportion of overall response, and its 80% confidence..

Additionally, we will evaluate overall response rate, defined as complete or partial response using RECIST or Lugano Criteria 2014 guidelines in a similar manner. We will also perform similar analyses using Immune Related RECIST (irRECIST). Duration of response, defined as the duration from the first documentation of clinical benefit to the first documented progressive disease or death of any cause, whichever occurs first, will also be analyzed. For patients alive and progression-free at the time of data cut off, duration of response will be censored as of the last tumor assessment date. Duration of response will only be evaluated for the subgroup of patients with a clinical benefit using the Kaplan-Meier method.

PFS is defined as the time from treatment initiation to documented disease progression. OS is defined as the time from the start of treatment until death due to any cause. For patients alive at the time of data cut-off, PFS and OS will be censored as of the last tumor assessment date or known to be alive, respectively. The PFS and OS will be estimated using the Kaplan-Meier method. The number, frequency, and severity of adverse events (as defined by the NCI Common Terminology Criteria for Adverse Events or CTCAE version 4.03) will be recorded.

Baseline percent PDL1 expression, TILs (sTILs, iTILs, and their ratio), and changes in T

cell subpopulations will be used as a continuous variable to predict clinical benefit or overall response rates using appropriate statistical summaries. Cox proportional hazards regression will be used to compare how these biomarkers are associated with PFS and OS as well.

Changes in these biomarkers will also be analyzed to assess for pharmacodynamic effects of treatment. Continuous variables will be analyzed using either paired t-tests, signed rank tests or repeated measures analysis of variance.

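### PFS as defined counts only documented progression, so a death without progression is not an event and has no handling rule

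*Combined protocol and SAP*

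**What the plan says.** The definition appears three times. Section 2.2.2 has "Progression Free Survival (PFS, defined as the time from treatment initiation to documented disease progression", assessed by RECIST 1.1 or Lugano. Section 6.5.2 repeats it, and section 10.3 says "PFS is defined as the time from treatment initiation to documented disease progression". Section 6.1.7 defines progression in solid tumours as "At least a 20% increase in the sum of diameters of target lesions, taking as reference the smallest sum on study", with an absolute increase of at least 5 mm, or as new lesions. Lymphoma follows the Lugano criteria in Appendix C.

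The censoring rule in 10.3 begins "For patients alive at the time of data cut-off, PFS and OS will be censored as of the last tumor assessment date" and sets the last date known alive for OS. PFS is to be estimated by Kaplan-Meier and is also a regression outcome: "Cox proportional hazards regression will be used to compare how these biomarkers are associated with PFS and OS as well".

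Three other passages bring death in:

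- Duration of response, in the paragraph of 10.3 just before the PFS definition, ends at "the first documented progressive disease or death of any cause, whichever occurs first".
- Section 2.2.5 sets the objective "To evaluate the proportion of patients alive and progression free at 24 weeks in this population", and 6.5.5 repeats it.
- Section 10.1 lists among the secondary endpoints "PFS at 24 weeks, time until death or disease progression", without calling the second item PFS.

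**The concern.** As written, the endpoint is time to progression under the label PFS. One possible outcome, death without documented progression, is assigned to neither side of the analysis. That outcome is plausible here: patients have relapsed or refractory advanced cancer, ECOG status up to 2 is allowed, and scans are 8 weeks apart.

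Two analysts could follow the protocol and report different PFS results. One who counts such deaths as events gets ordinary PFS. One who follows the definition literally and censors them gets a curve, a median and a 24-week reading that are too high, and drops those deaths as events from the Cox biomarker models. The 24-week proportion in 2.2.5 already treats death as failure, so one report could carry two 24-week figures that disagree for the same patients.

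**Working it through.** **Text check.** The documents give no event count, power or assumed rate for PFS, so there is no plan figure to reproduce.

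| Endpoint | Is death an event? | Who is censored |
|---|---|---|
| PFS (2.2.2, 6.5.2, 10.3) | Not named | Patients alive at cut-off |
| Duration of response (10.3) | Yes | Patients alive and progression-free at cut-off |
| 24-week proportion (2.2.5, 6.5.5) | Yes, counts as failure | Not stated |
| Second item quoted from 10.1 | Yes | Not stated |
| irPFS (2.2.3, 6.5.3) | Event not defined | Not stated |

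**Size if such deaths are censored at the last tumour assessment.** From the documents: n=10 patients with mutations (10.2), 3+6+6=15 treated in all, and scans every 8 weeks (Table 5, footnote j). The patient patterns, medians and death shares are assumptions.

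*Small-sample examples (24-week proportion against Kaplan-Meier)*

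- A, n=10: 2 die before scan 1, 4 progress, 4 are progression-free. Proportion 4/10 = 40%. Kaplan-Meier has 8 at risk: 4/8 = 50%.
- B, n=10: 4 progress at scan 1, 2 die before scan 2, 1 progresses at scan 2, 3 are progression-free. Proportion 3/10 = 30%. Kaplan-Meier: 6/10 × 3/4 = 45%.
- C, n=10: 1 dies before scan 1, 5 progress, 4 are progression-free. Proportion 4/10 = 40%. Kaplan-Meier: 4/9 = 44.4%.
- D, n=15: 2 die before scan 1, 7 progress, 6 are progression-free. Proportion 6/15 = 40%. Kaplan-Meier: 6/13 = 46.2%.

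*Exponential model.* Let m be the median PFS in months and d the share of first events that are deaths without progression. The chance of no event over one 56-day scan interval is

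q = exp(−ln2 × 56 / (30.44 m)).

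True 24-week PFS is q³. If a death is censored at the previous scan, that patient leaves the risk set for the interval. The Kaplan-Meier factor becomes q / [q + (1−d)(1−q)] = q / [1 − d(1−q)], and the 24-week reading is its cube.

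For m=3, q = exp(−0.425) = 0.654 and q³ = 27.9%. With d=0.15 the factor is 0.6537 / (1 − 0.15 × 0.3463) = 0.6895, and its cube is 32.8%.

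| Assumed median (months) | True 24-week PFS | d=5% | d=15% | d=30% |
|---|---|---|---|---|
| 2 | 14.8% | 15.9% | 18.4% | 23.3% |
| 3 | 27.9% | 29.4% | 32.8% | 38.8% |
| 4 | 38.4% | 40.0% | 43.6% | 49.7% |
| 6 | 52.9% | 54.4% | 57.7% | 63.1% |

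Across these medians the excess is 1.1–1.6, 3.6–5.1 and 8.6–11.2 percentage points. It is zero when d=0.

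*Median.* With constant hazards and continuous observation, censoring the deaths multiplies the median by 1/(1−d). That is 1.11, 1.25 and 1.43 for d = 10%, 20% and 30%.

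*Sampling error.* The exact 95% interval for 4/10 is 12.2% to 73.8%.

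**The case against.** The best reply is that the plan never tells anyone to censor these deaths. Its censoring rule is limited to living patients, and 10.1 names an endpoint that includes death, so the intended reading can be recovered. The 24-week endpoint handles death correctly already. Part of this stands: the passages do lean towards death as an event, and every figure above depends on an analysis the plan does not prescribe. It does not close the gap. The item in 10.1 is listed separately from PFS at 24 weeks and carries no rule, and the definition in the analysis section itself omits death.

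Second, some deaths might be classed as progression on clinical grounds. Section 4.7.1 recognises clinical signs of progression, and 4.8 allows follow-up by telephone. That may shrink the affected group, but 2.2.2 and 6.5.2 tie PFS to RECIST or Lugano.

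Third, examples A, C and D depend on deaths before the first scan. Section 10.3 restricts its ITT population to evaluable patients without defining the term. If those patients were not evaluable, the contrast in these examples would disappear. That is fair. Example B does not have this weakness.

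Finally, PFS here is descriptive, and the shifts are small beside the sampling error. That limits the consequence, although the error, where it occurs, is always in the favourable direction. Nor is PFS the only progression endpoint that is silent on death: irPFS has no defined event at all.

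**Conclusion.** The concern holds. The PFS definition is wrong as written: it leaves out death, gives no rule for a death without documented progression, and conflicts with duration of response and the 24-week endpoint. If the written definition is followed and such deaths are censored, 24-week PFS is overstated by about 1 to 11 percentage points, for assumed medians of 2 to 6 months and assumed death shares of 5% to 30%. There is no overstatement if no such deaths occur or if the analyst counts them as events. No decision rule uses PFS, so the consequence is limited to the reported PFS results and the exploratory Cox models. It should be fixed, and it does not threaten the trial's main conclusions.

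**What to change.** In 2.2.2, 6.5.2 and 10.3, define PFS as the time from treatment initiation to the first of progression or death from any cause. Define irPFS the same way, with progression by irRECIST. Replace the PFS censoring rule so that patients alive and progression-free are censored at their last tumour assessment, as is already done for duration of response. In 10.1, say that the item combining death and progression is PFS.

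Three separable clarifications could go into the same edit:

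- State that treatment initiation is induction day 1.
- State that RECIST 1.1 or Lugano progression is dated at the first scan showing it, and reconcile Table 5 footnote j, which asks for a confirmatory scan, with 6.3.1, which says RECIST 1.1 has none.
- Let the 24-week classification window include the Cycle 7 Day 1 scan. This is nominally day 175 from induction (7 + 6 × 28). Allowing 7 days early for the scan and ±3 days for the visit gives about days 165–178.

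The change is to wording only and needs no new data, because 4.8 and 4.9 already follow patients for survival and progression. It does need the amendment review described in 11.2. Reported PFS may come out slightly less favourable.

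### Section 10.3 censors PFS for every patient alive at cut-off, without requiring that the patient be progression-free, which conflicts with its own definition of the PFS event

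*Combined protocol and SAP*

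**What the plan says.** Section 10.3 defines the endpoint first: "PFS is defined as the time from treatment initiation to documented disease progression". Sections 2.2.2 and 6.5.2 give the same definition and no censoring rule.

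The censoring rule in 10.3 covers PFS and OS in one sentence: "For patients alive at the time of data cut-off, PFS and OS will be censored as of the last tumor assessment date". The sentence goes on to assign the dates respectively: last tumor assessment for PFS, last known alive for OS. Only the date differs between the two endpoints; the condition is shared.

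The rule for duration of response, in the paragraph before, is stricter: "For patients alive and progression-free at the time of data cut off, duration of response will be censored". The Statistical Methodology part of the study summary words that rule in the same way and gives no censoring rule for PFS.

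Section 10.1 lists "PFS at 24 weeks, time until death or disease progression" among the secondary endpoints, again without a censoring rule. Section 10.3 names Kaplan-Meier as the estimator for PFS and OS, and uses both as outcomes in Cox models for the biomarkers.

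**The concern.** A patient who has progressed and is still alive at cut-off meets both the event definition and the censoring condition, and the plan does not say which governs. If the censoring rule is followed, the only PFS events left are patients who both progressed and died before cut-off. Two patients with the same progression scan are then treated differently because of what happened afterwards. That censoring is informative, and it removes events from the curve.

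Such patients will exist. Section 4.8 follows patients for survival and progression after treatment, up to 3 years from its start. Section 4.7.1 allows treatment to continue after a first progression, and footnote j of Table 5 asks for a confirmatory scan within 8 weeks. Where that scan is done, the last tumor assessment falls after the progression date. The rule then also credits time after progression as progression-free.

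**Working it through.** The plan states no PFS assumption, event count or cut-off, so there is no figure to reproduce. The check has three parts.

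**1. The rules side by side (Section 10.3).**

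| Endpoint | Event | Condition for censoring | Censoring date |
|---|---|---|---|
| Duration of response | progression or death | alive and progression-free | last tumor assessment |
| PFS | documented progression | alive | last tumor assessment |
| OS | death | alive | last known alive |

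In the first and third rows no patient can meet both the event and the censoring condition. In the PFS row a living patient with progression meets both. No other section restores the missing condition.

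**2. A hand example.** Take ten invented patients, all with documented progression: six at week 8, three at week 16, one at week 24. Four are alive at cut-off: two of the week-8 group, one of the week-16 group and the week-24 patient. The Kaplan-Meier estimate is S(t) = product of (1 − d/n) over event times.

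- Progression counted: (1 − 6/10) = 0.40; × (1 − 3/4) = 0.10; × (1 − 1/1) = 0. Ten events, median 8 weeks.
- Rule as written: (1 − 4/10) = 0.60; two censored at week 8, leaving four at risk; × (1 − 2/4) = 0.30; the week-24 patient is censored. Six events, median 16 weeks, and the curve stays at 30%.

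**3. Size under stated assumptions.** From the documents: treatment starts with a 7-day induction, and scans begin at Cycle 3 Day 1 and repeat every 8 weeks. That puts them at weeks 9, 17, 25 and so on. Assumed, because the plan gives nothing: exponential time to progression with median 2, 3 or 4 months; exponential survival after progression, with its median chosen so that the two medians sum to 8 or 12 months; equal follow-up for all patients; deaths before a documenting scan censored at the last scan; no confirmatory scan. There were 200,000 simulated patients per scenario. The share lost is (documented progressions in patients alive at cut-off) / (all documented progressions).

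| Follow-up | Share of documented progressions censored | Kaplan-Meier PFS at week 24, 3-month median: progression counted → as written | Same, just after the week-25 scan |
|---|---|---|---|
| 12 months | 34–57% | 43–45% → 58–68% | 29–31% → 48–60% |
| 36 months | 1–11% | 43–45% → 45–47% | 29–31% → 31–33% |

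If deaths without documented progression are instead counted as PFS events, the rule removes 28–53% of all events at 12 months and 1–10% at 36 months. Adding a confirmatory scan could only raise the as-written curve: living progressors would stay in the risk set longer while the events stay the same.

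A different set-up gives the same direction. It assumed scans every 8 weeks, uniform entry over 26 weeks, cut-off 26 weeks after the last entry, median time to progression 8–16 weeks and median survival after progression 16–39 weeks. The rule dropped 37–69% of documented progressions and moved 24-week Kaplan-Meier PFS from 14–41% to 38–75%.

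**The case against.** The strongest reply is that no experienced analyst would do this. Censoring ordinarily applies to patients without the event, the definition stands in the same paragraph, and the sentence looks like PFS and OS compressed into one line. That is probably right about intent. A reader might infer that the plan means to discard progressions in living patients, and the documents do not support that. What stands is that definition and rule give opposite answers for the same patient, while the neighbouring rule shows that the authors had the correct wording.

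Three further inferences are tempting and should not be drawn.

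- *That the 24-week endpoint is inflated.* Sections 2.2.5 and 6.5.5 define it as a status: "To evaluate the proportion of patients alive and progression free at 24 weeks in this population". A patient who progressed at week 9 is not progression-free at week 24, whatever the PFS censoring rule says. The endpoint is affected only if it is read from a Kaplan-Meier curve under this rule. Section 10.1 speaks of PFS at 24 weeks, but no section names that estimator.
- *That PFS will be cut off early.* The early analysis in Sections 1.9, 4.3.3 and 10.2 is of response rate at first imaging. Section 6.5.2 adds unspecified other measures at that scan, but no PFS cut-off is given, and Section 4.8 plans follow-up to 3 years. With 6 months of follow-up the same simulation loses about two-thirds to 82% of progressions, but that applies only if PFS is analysed then. Uniform 6-month follow-up also fits poorly: Appendix E records six patients treated at the MTD by February 2019, and the current version is dated March 2020.
- *That the trial's conclusion is at risk.* The MTD and the response-rate success rule do not use this sentence. PFS is secondary, with no hypothesis or decision rule, in about 9 + 6 = 15 patients.

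**Conclusion.** The rule is wrong as written. It lacks the progression-free condition, contradicts the definition in its own section, and biases Kaplan-Meier PFS upward if followed. In the Cox models it turns the outcome into progression followed by death before cut-off, so a biomarker's association with PFS is mixed with its association with survival after progression.

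The direction does not rest on the assumptions; the size does. It depends mainly on the unstated cut-off: about 34–57% of documented progressions lost at 12 months, and about 1–11% at the planned 36 months, under the exponential medians given above. If PFS is analysed only after full follow-up, the practical effect is small. In so few patients, however, reclassifying even a few events moves the curve visibly. It should be corrected, but it is a drafting error in a secondary, descriptive analysis.

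**What to change.** Replace the shared sentence in Section 10.3 with two:

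*Patients alive and without documented progression at data cut-off are censored for PFS at the last tumor assessment date. Patients alive at data cut-off are censored for OS at the date last known alive.*

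Make this edit together with a separate correction to the same sentences. The 10.3 definition of PFS omits death while 10.1 names it, so a patient who dies without documented progression currently has neither an event nor a censoring rule. The wording above does not settle that case by itself.

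The cost is one sentence in one section. No data collection, sample size or success criterion changes. It should be settled before the PFS data are examined.

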Sample size	
The initial study design was to accrue a total of up to 50 patients for 48 evaluable) to the study in two phases: dose escalation and dose expansion. The original design anticipated a total of 6-18 patients with advanced solid tumors or lymphoma in the dose escalation phase; 9 patients were enrolled, including 3 at lowest dose and 6 that were treated at the MTD of 400 mg BID. It is still planned for 6 patients with advanced solid tumors and lymphoma with mutations in selected DNA repair genes to be enrolled into the expansion cohort to receive the maximum tolerated dose of veliparib in combination with nivolumab. However, due to funding issues, the study will perform an early analysis of preliminary efficacy after the next 6 patients are enrolled in the expansion cohort, all with the genetic mutation. Of the 6 patients already at MTD, 4 have the genetic mutation. No responses were observed in any patient at MTD. Total number of patients at the end of adding 6 more patients with mutation will be $4+6=10$. The study will be considered a “success” if the lower exact 90% confidence limit is $> 10\%$, i.e. when 3 or more successes are observed. . According to the modified plan for the current trial, the study will be closed after the 6 additional patients will have been recruited.”

--------------------	---

NU Study Number: NU 16MH03
BMS Study Number: CA 209-783
Abbvie Study Number: A15-831

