2.3 Exploratory Objectives & Endpoints

The main goals of the objectives listed below are to identify predictive biomarkers beyond the genetic mutations by which treatment is assigned, and to identify resistance mechanisms to the nivolumab and veliparib combination using additional genetics and tumor immunology-based assessment platforms

Biomarker tests will be done at baseline using fresh tissue (or archived if a fresh biopsy is not feasible), as well as from blood samples at Induction Day 1, Cycle 1 Day 1, Cycle 3 Day 1, and the End of Treatment visit.

2.3.1 To evaluate if any of the following predict response to veliparib in combination with nivolumab:

- Tissue PD-L1 protein expression
- Immune cell infiltration markers

2.3.2 To demonstrate the pharmacodynamic effects of veliparib and nivolumab on biomarkers including PD-L1, TILs, T cell subpopulations, and T cell receptor genotype.

2.3.3 To assess the dynamic change in both immune and genomic biomarkers in blood that may correlate with response to veliparib.

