6.1.5 Measurable Disease

Measurable lesions are defined as those that can be accurately measured in at least one dimension (longest diameter to be recorded) as ≥ 20 mm (≥ 2 cm) by chest x-ray or as ≥ 10 mm (≥ 1 cm) with CT scan, MRI, or calipers by clinical exam. All tumor measurements must be recorded in millimeters (or decimal fractions of centimeters).

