10.2 Sample Size and Accrual

The initial study has recruited 3 patients at the lower dose and 6 at the MTD. Of these 6 at the MTD, 4 have genetic mutation of interest, and 2 do not. The study will, due to lack of funding and other reasons recruit 6 more patients with genetic mutation of interest. The response rate will be computed separately for 4+6 = 10 patients with genetic mutation.

Dose Escalation Phase

The expected number of patients in the dose escalation phase will be in the range of 6 to

18 based on the 3+3 design.

Expansion Cohort

The initial study design was to accrue a total of up to 50 patients (for 48 evaluable) to the study in two phases: dose escalation and dose expansion. The original design anticipated a total of 6-18 patients with advanced solid tumors or lymphoma in the dose escalation phase; 9 patients were enrolled, including 6 that were treated at the MTD of 400 mg BID. Due to funding issues, the study will perform an early analysis of preliminary efficacy after the next 6 patients are enrolled in the expansion cohort.

As stated above, in **the modified plan for expansion cohort**, will accrue 6 new patients with genetic alteration for early preliminary efficacy assessment, which together with 4 previously treated patients with genetic mutation will provide total of 6+4=10 patients, with genetic mutation. ORR will be computed at the first imaging (8 weeks). Preliminary efficacy will be evaluated by RECISTv 1.1. As exploratory analysis, irRECIST will be used to obtain preliminary efficacy as well. All ORR will use the first imaging time point whether RECIST or irRECIST.

The study will be considered a success if the lower 90% exact confidence bound will be > 10% , i.e. if three or more successes out of n=10 are observed.

I According to the modified plan for the current trial, the study will be closed after the 6 additional patients will have been recruited.”

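### The exploratory biomarker analysis relates markers to tumour effect only through yes/no outcomes and survival models; adding a rank correlation with recorded tumour-size change would be a cheap gain

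*Combined protocol and SAP*

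**What the plan says.** Exploratory objective 2.3.1 is "To evaluate if any of the following predict response to veliparib in combination with nivolumab", and names tissue PD-L1 and immune cell infiltration markers. Section 10.3 says that baseline percent PD-L1, TILs (stromal, intraepithelial and their ratio) and changes in T-cell subpopulations "will be used as a continuous variable to predict clinical benefit or overall response rates using appropriate statistical summaries". The next sentence adds that "Cox proportional hazards regression will be used to compare how these biomarkers are associated with PFS and OS as well". No test, significance level, sidedness, effect size or power is stated for this work.

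Response in solid tumours is a cut on a continuous measure. Section 6.1.7 defines partial response as "At least a 30% decrease in the sum of the diameters of target lesions, taking as reference the baseline sum diameters". The underlying sizes are kept: section 6.1.5 says "All tumor measurements must be recorded in millimeters (or decimal fractions of centimeters)". Section 6.3 also applies irRECIST to both solid tumours and lymphoma. Its tumour burden is a sum of single diameters to which new measurable lesions are added.

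On numbers, section 10.2 says "The initial study has recruited 3 patients at the lower dose and 6 at the MTD", and that the study will "recruit 6 more patients with genetic mutation of interest". The Study Summary, under sample size, reports "No responses were observed in any patient at MTD". Results for the three lower-dose patients are not given.

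**The concern.** The markers stay continuous, but the tumour outcome is reduced to two categories in a very small sample where responses are already known to be scarce. A response yes/no comparison needs responders, and there may be none or one. A patient whose lesions shrink by 25% and one whose lesions grow by 15% both count as non-responders, although a marker that tracks tumour change would separate them. At stake is how much objective 2.3.1 can learn from the tissue and blood collected for it. The dose finding and the response-rate success rule do not depend on this analysis.

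**Working it through.** **The plan's own figure.** The plan gives no power or sample size for the biomarker work. Its one computable figure nearby is the success rule of 3 or more responses in 10. The one-sided 90% exact lower bound is 11.6% for 3/10 and 5.5% for 2/10, so the rule reproduces on that reading. It has no bearing on the biomarker question.

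**Inputs from the documents.** Patients: 3 + 6 + 6 = 15. Known non-responders at the MTD: 6. Patients who could still supply a responder, if those six do not change: 15 − 6 = 9.

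**Inputs assumed, because the plan states none.** True response rate 10% to 30%; two-sided 5% level; correlation 0.4 to 0.7 between marker and tumour change (bivariate normal); one marker; all 15 patients with data; clinical-benefit rate 40-50%.

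**Step 1: how many responders to expect.** P(at most 1 of m) = (1−p)^m + m·p·(1−p)^(m−1).

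| True rate p | m = 9 | m = 6 (if the 3 lower-dose patients also did not respond) |
|---|---|---|
| 10% | 0.387 + 0.387 = 77% | 0.531 + 0.354 = 89% |
| 20% | 0.134 + 0.302 = 44% | 0.262 + 0.393 = 66% |
| 30% | 0.040 + 0.156 = 20% | 0.118 + 0.303 = 42% |

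The first term in each sum is the chance of no responder at all.

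**Step 2: what so few responders allow.** With r responders of 15, the smallest two-sided exact rank p is 2/C(15, r).
- r = 0: no comparison exists.
- r = 1: 2/15 = 0.133, even if the responder has the most extreme marker value.
- r = 2: 2/105 = 0.019.

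**Step 3: power without conditioning on 0/6.** Simulation at n = 15 compares Spearman correlation with percent change against an exact rank-sum test of the marker by the yes/no outcome.

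| Correlation | Percent change | Response cut, rates 10% to 30% | Clinical-benefit cut, rates 40-50% |
|---|---|---|---|
| 0.4 | 29% | 7% to 18% | 18-19% |
| 0.6 | 61% | 15%, 29%, 36% | 39-41% |
| 0.7 | 80% | 19% to 50% | 56-58% |

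Relative loss is 1 − (power after the cut)/(power with percent change). At correlation 0.6 the response cut loses 1 − 15/61 = 75%, 1 − 29/61 = 52% and 1 − 36/61 = 41%. Over all correlations, and allowing for simulation and test choice, the loss is about 35-77%: the low end at a 30% response rate, the high end at 10%. For clinical benefit it runs from 1 − 58/80 = 27.5% to 1 − 18/29 = 38%.

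**Step 4: power with six patients fixed as non-responders.** At correlation 0.6, percent change has 58%, 56% and 56% power, against 7%, 16% and 25% for the response cut at rates of 10%, 20% and 30%. The losses, from unrounded powers, are 1 − 0.066/0.581 = 89%, 1 − 0.158/0.557 = 72% and 1 − 0.247/0.559 = 56%. Over correlations 0.4 to 0.7 the range is about half to 90%.

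**Step 5: what lowers all of these.** Tissue is optional (section 9.1), so fewer than 15 patients may have PD-L1 and TIL results. At n = 10 the Spearman power is 41% at correlation 0.6 and 19% at 0.4. With a Bonferroni correction over four markers at n = 15 it is 39% and 13%.

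**The case against.** Several objections have force.

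- **No test or threshold is set.** The plan names neither a rank test nor a 5% level, so it cannot be faulted for missing one. This stands: the 0.133 shows how little one responder can say, not that a planned test fails. A response comparison with no responders remains impossible under any method.
- **Response is not the only outcome.** A reader might infer that all the biomarker work loses half its power or more. The documents do not support that. Clinical benefit is named in the same sentence and loses only about a third, and the Cox models for PFS and OS are not yes/no analyses. They do not use the amount of shrinkage, however. Even for response alone, a loss of half or more at a 30% rate holds only after allowing for the known 0/6; without that it is about 35-44%.
- **The six may not be final.** Section 10.3 uses maximum response before progression, while section 10.2 uses the first scan. The documents do not say whether the six were still on treatment. Step 1 therefore rests on their staying non-responders.
- **Percent change is not response.** Target-lesion change alone would rank a patient with shrinking targets and a new lesion as favourable, and it mixes histologies. This stands, and is why the fix uses irRECIST burden with a worst-rank rule and adds to the planned outcomes without replacing them.
- **The gain can be small in absolute terms.** Against clinical benefit at correlation 0.4 it is about 10 points (29% against 19%), and less with fewer patients. This also stands.

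**Conclusion.** The point holds as a cheap improvement to an exploratory analysis. Section 10.3 leaves recorded tumour-size change unused where responders may number none or one: the chance of at most one among the nine is 77%, 44% and 20% at true rates of 10%, 20% and 30%. The power losses in steps 3 and 4 rest on the assumed level, correlations, rates, normality, single marker and full 15 patients; the plan supplies none of these.

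It would go too far to conclude that objective 2.3.1 cannot be addressed as planned, or that percent change would settle it. Clinical benefit and the Cox models remain, a response among the lower-dose patients is not ruled out, and power is modest even with the better measure.

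**What to change.** In section 10.3, add a Spearman rank correlation of each baseline biomarker with percent change in irRECIST tumour burden from baseline to the first (8-week) scan. Because section 6.3 already applies that burden to solid tumours and lymphoma and adds new measurable lesions, both groups can be ranked on one measure. Rank as worst any patient who dies or clinically progresses before the scan, or who has unequivocal progression through new non-measurable lesions. Report each estimate with a confidence interval and the number of patients contributing, and label the results exploratory. Keep the response, clinical-benefit and Cox analyses. The T-cell changes in 10.3 are not baseline markers and can stay with those analyses.

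The cost is a few lines of text, one derived variable and one more exploratory analysis, with no new scans, samples or patients. The downside to state is that percent change across mixed histologies is not identical to response.
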